9.1.2 Impact of Study Treatment

The impact the event had on the study treatment will be assessed as either: none, study treatment interrupted, study treatment discontinued, or not applicable. The "not applicable" assessment will be used only when the subject is no longer in the treatment extension phase of the protocol, or if the outcome of the event was "death".

9.1.3 CTCAE Grade (Severity) Assessment

The investigator will carefully evaluate the comments of each subject and the response to treatment in order to judge the true nature and severity of the AE. The question of the relationship of AEs to study drug should be determined by the investigator after thorough consideration of all available facts. To assess severity, the investigator will use the DAIDS AE grading table (for adverse events as well as any injection site reactions refer to [Section 17.2](#) and [Section 17.3](#)).

If a severity rating is not defined in the DAIDS AE grading table for a particular AE, severity will be rated according to the guidelines outlined in CTCAE v4.03. The general guidelines for assessing the AE grade appear below. Full guidelines may be obtained at <http://evs.nci.nih.gov/ftp1/CTCAE>.

Table 9-1: CTCAE v4.03 General Guidelines

Grade	Description
Grade 1	Mild; asymptomatic or mild symptoms; clinical or diagnostic observations only; intervention not indicated.
Grade 2	Moderate; minimal, local, or noninvasive intervention indicated; limiting age-appropriate instrumental activities of daily living (ADL)*.
Grade 3	Severe or medically significant but not immediately life-threatening; hospitalization or prolongation of hospitalization indicated; disabling; limiting self care ADL†.
Grade 4	Life-threatening consequences; urgent intervention indicated.
Grade 5	Death related to AE.

*Instrumental ADL refer to preparing meals, shopping for groceries or clothes, using the telephone, managing money, etc.

†Self care ADL refer to bathing, dressing and undressing, feeding self, using the toilet, taking medications, and not bedridden.

-Common Terminology Criteria for Adverse Events (CTCAE), v4.03: June 14, 2010

9.1.4 Causality Assessment

Adverse events will be assigned a relationship (causality) to the study treatment. The Principal Investigator (PI) must review each AE and make the determination of relationship of the event to the study treatment. Relationship of AEs to study treatment will be classified as follows:

- Definitely related:** This category applies to those AEs that the Investigator feels are incontrovertibly related to the study treatment. An AE may be assigned an attribution of definitely related if or when it meets all of the following criteria: (1) it follows a reasonable temporal sequence from administration of the study treatment; (2) it could not be reasonably explained by the known characteristics of the subject's clinical state, environmental or toxic factors, or other modes of therapy administered to the subject; (3) it follows a known response pattern to treatment with the study treatment.
- Probably related:** This category applies to those AEs which, after careful medical

consideration at the time they are evaluated, are felt with a high degree of certainty to be related to the study treatment. An AE may be considered probable if or when (must have three): (1) it follows a reasonable temporal sequence from administration of the study treatment. (2) It could not readily have been produced by subject's clinical state, environmental or toxic factors, or other therapies administered to the subject. (3) Disappears or is decreased upon discontinuation of the study treatment. (4) It follows a known response pattern to treatment with the study treatment.

3. **Possibly related:** This category applies to those AEs which, after careful medical consideration at the time they are evaluated, are judged unlikely but cannot be ruled out with certainty to the study treatment. An AE may be considered possible if or when (must have two): (1) it follows a reasonable temporal sequence from administration of the study treatment. (2) It could not readily have been produced by subject's clinical state, environmental or toxic factors, or other therapies administered to the subject. (3) Disappears or is decreased upon discontinuation of the study treatment. (4) It follows a known response pattern to treatment with the study treatment.
4. **Remotely related:** In general this category can be considered applicable to those AEs which, after careful medical consideration at the time they are evaluated, are judged likely to be unrelated to the study treatment. An AE may be considered unlikely if or when (must have two): (1) it does not follow a reasonable temporal sequence from administration of the study treatment. (2) It could not readily have been produced by subject's clinical state, environmental or toxic factors, or other therapies administered to the subject. (3) Disappears or is decreased upon discontinuation of the study treatment. (4) It does not follow a known response pattern to treatment with the study treatment.
5. **Unrelated:** This category applies to those AEs which, after careful consideration at the time they are evaluated, are clearly and incontrovertibly due to extraneous causes (disease, environment, etc.) and determined with certainty to have no relationship to the study treatment.

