8.5.3 Data and Information Provided to DMC

The DMC will receive: AEs, SAEs, labs, ECGs, vital signs, and all other safety related variables identified per the DMC Charter. No inferential statistics will be conducted for this interim analysis.

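### Two of the four criteria for 'Remotely related' keep the wording that supports a drug relationship, so the causality categories overlap and leave a gap (Protocol 9.1.4)

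*Protocol*

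**What the plan says.** Section 9.1.4 has five categories. 'Definitely related' applies "if or when it meets all of the following criteria: (1) it follows a reasonable temporal sequence", together with the absence of another reasonable explanation and a known response pattern. 'Probably related' needs three, and 'Possibly related' two, of the same four supportive features, the last two being "3) Disappears or is decreased upon discontinuation of the study treatment. (4) It follows a known response pattern".

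'Remotely related' is for events that "are judged likely to be unrelated to the study treatment". Its rule begins "An AE may be considered unlikely if or when (must have two): (1) it does not follow a reasonable temporal sequence". Criterion 2 then repeats the 'Probably' and 'Possibly' wording that the event could not readily have another cause. The last two criteria read "3) Disappears or is decreased upon discontinuation of the study treatment. (4) It does not follow a known response pattern".

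'Unrelated' has no numbered criteria. It requires an event to be clearly due to an extraneous cause and "determined with certainty to have no relationship to the study treatment".

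**The concern.** In a category for events that are probably not due to the drug, each criterion should count against the drug. Criteria 1 and 4 do. Criteria 2 and 3 count for it, in the words used for the two stronger categories. Since 1 and 4 were reversed, this looks like an unfinished edit. Two things follow from the listed criteria.

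- **Overlap.** An event with no ready alternative cause that abates on stopping already has two 'Remotely' criteria, although the same two features count towards 'Probably'. This can arise only where treatment was stopped or interrupted.
- **Gap.** An event with plausible timing, a ready alternative cause, no abatement and no known pattern has one 'Possibly' criterion and one 'Remotely' criterion. It meets neither rule, and the only category left demands certainty. The same holds for an event whose only supportive feature is a known pattern. This does not depend on treatment being stopped.

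The grade feeds the summary of treatment-emergent events by relationship (8.7.5.1), and related events are among those the monitoring committee reviews (section 12).

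**Working it through.** No design figure is involved, so the check is one of logic.

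**Inputs (section 9.1.4).** Code each feature 1 if present and 0 if absent: T = reasonable timing, N = no ready alternative cause, D = abates on stopping, P = known response pattern.

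| Feature | Counts towards 'Probably' and 'Possibly' if | Counts towards 'Remotely' if |
|---|---|---|
| T | present | absent |
| N | present | **present** |
| D | present | **present** |
| P | present | absent |

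**Rules**, reading 'must have k' as at least k:

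- Definitely: T = N = P = 1 (its second criterion is worded slightly differently and is taken as N)
- Probably: T + N + D + P ≥ 3
- Possibly: T + N + D + P ≥ 2
- Remotely as written: (1−T) + N + D + (1−P) ≥ 2
- Remotely with both criteria reversed: (1−T) + (1−N) + (1−D) + (1−P) ≥ 2

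**Enumeration.** There are 2^4 = 16 patterns, written TNDP. Definitely is met by 2, Probably by 5, Possibly by 11 and Remotely as written by 11.

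- *Probably and Remotely, as written:* 1111 scores 0+1+1+0 = 2, 1110 scores 0+1+1+1 = 3, and 0111 scores 1+1+1+0 = 3. The other two Probably patterns, 1101 and 1011, score 1. So 3 of 5 overlap, and 1111 also meets Definitely.
- *Neither Possibly nor Remotely, as written:* the 5 patterns that fail Possibly are 0000, 1000, 0100, 0010 and 0001. Their Remotely scores are 2, 1, 3, 3 and 1. So 1000 (timing only) and 0001 (pattern only) meet no numbered rule.

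| 'Remotely' wording | Probably and Remotely | Definitely and Remotely | Neither Possibly nor Remotely | Possibly and Remotely |
|---|---|---|---|---|
| As written | 3 | 1 | 2 | 8 |
| Criterion 2 reversed only | 3 | 0 | 0 | 6 |
| Criterion 3 reversed only | 3 | 1 | 0 | 6 |
| Both reversed | 0 | 0 | 0 | 6 |

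Reversing one criterion closes the gap but leaves the Probably overlap at 3, so both changes are needed. The 6 remaining ties are the patterns with exactly two supportive features: both thresholds are two of four.

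**Treatment continues, so D cannot be judged.** With T, N and P only there are 8 patterns. As written, no pattern meets both Probably and Remotely. Of the 4 that fail Possibly, 2 also fail Remotely (100 and 001 in TNP order). With criterion 2 reversed, none does.

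**Sensitivity: 'must have k' read as exactly k.** As written: Probably and Remotely 0, Definitely and Remotely 1, Possibly and Remotely 4, no numbered rule met 4. With both reversed: 0, 0, 6 and 5.

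**The case against.** The strongest reply is that the numbered lists are only guides. Each category opens with a judgement, the criteria say an event may be considered to belong, and section 9.1.3 says the relationship "should be determined by the investigator after thorough consideration of all available facts". An investigator can put a timing-only event in 'Remotely related' on the opening sentence. This stands: the slip sets the list against the judgement it should guide, but forces no wrong grade. It does not make the list right, and the must-have-two condition pulls the other way.

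Second, the counts depend on the at-least reading. On the exactly reading the Probably overlap disappears, and the fix takes the gap from 4 to 5 patterns and the Possibly ties from 4 to 6. But on that reading an event with all four features against the drug would not qualify as remotely related once the criteria are reversed. At least is the natural meaning, and the text as written is defective on either reading.

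Third, the fix does not give a cleanly discriminating scale. That is also true: 6 patterns stay tied between 'Possibly' and 'Remotely', and the opening sentences of both speak of an unlikely relationship.

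Fourth, little depends on the grade. "The DMC will receive: AEs, SAEs, labs, ECGs, vital signs, and all other safety related variables", with no restriction to related events. The protocol does not say which categories count as related for the committee, so no effect there can be shown. Events leading to discontinuation, where the overlap could arise, are summarised separately (8.7.5.1). No safety endpoint uses causality (8.2.3), and no inferential safety statistics are planned (8.7.5). All this limits the weight of the point.

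**Conclusion.** The concern holds. Criteria 2 and 3 of 'Remotely related' contradict the category's stated purpose. On the at-least reading, 3 of the 5 'Probably' patterns also meet 'Remotely', one of them meeting 'Definitely' too, and 2 of the 5 patterns below 'Possibly' meet no numbered rule. Both defects vanish when both criteria are reversed. The counts describe patterns of criteria, and nothing in the protocol says how often each occurs. The practical effect is confined to a descriptive table and the consistency of grading between investigators, in a single-arm study of up to 28 subjects. This is a low-priority correction to an adverse event definition and does not touch the efficacy analysis.

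**What to change.** In 'Remotely related' only, reverse two criteria:

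- Criterion 2: the event *could* readily have been produced by the other causes already listed there.
- Criterion 3: the event *does not* disappear or decrease when study treatment is discontinued.

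Leave thresholds, opening sentences and the other categories as they are. The two-feature ties with 'Possibly related' stay with the investigator's judgement.

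The cost is two phrases at the next amendment and a one-line note to sites. No regrading of recorded events is proposed, so the relationship table will combine events graded under both wordings. For a descriptive table that is a small price.

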9.1.5 Treatment Given as a Result of the Event

The event impact in terms of treatment provided will be as either: none, medication administered, non-medication therapy administered, surgery, or other (with a specification).

9.1.6 Outcome Assessment

The outcome of the event will be assessed as either: resolved, resolved with sequelae, ongoing, or death. Only one AE per subject is allowed to have an outcome assessment as "death." If there are multiple causes of death for a given subject, only the primary cause of death will have an outcome of death.

9.1.7 Expected / Anticipated Adverse Events

The most common potential study drug-related adverse reaction reported is mild headache. Other adverse events likely to be related to the drug include mild to moderate diarrhea, nausea, and fatigue.

9.1.8 SC Injection-related Events

SC and IV injections of concentrated protein materials can be associated with injection-related AEs that impact the ability to safely and successfully deliver the drug. Local injection-site reactions may include pain/discomfort, induration, erythema, nodules/cysts, pruritus, ecchymosis, etc. For SC injections, bleeding, absorption of the drug, leakage of drug, and induration at the local injection site can be additional complications. Other AEs that are common to monoclonal antibody-based therapies are chills, headache, backache, malaise, fever, pruritus, rash, nausea, tingling, and hypertension.

SC injection-related events will be monitored according to the guidelines provided in [Section 17.2](#) (Division of AIDS Table for Grading the Severity of Adult and Pediatric Adverse Events [DAIDS AE Grading Table]). Injection-site reactions thought to be directly related to the injection are considered to be AEs of special interest, and a separate guideline for the acquisition of data related to this AE of special interest is provided in [Section 17.3](#).

For subjects who develop grade 1 or grade 2 events, continue therapy as per protocol. If a subject chooses to discontinue study treatment, the site should notify the protocol team leadership, and encourage the subject to complete any remaining study visits until the toxicity resolves.

For subjects who develop grade 3 events following study drug injection, the subject should be reevaluated closely until the AE returns to Grade ≤ 2 , at which time study treatment may be reintroduced at the discretion of the site investigator. If the *same* Grade 3 AE recurs following the next administration of study drug, study treatment must be permanently discontinued. Subjects experiencing Grade 3 AEs requiring permanent discontinuation of study treatment should be followed closely for resolution of the AE to Grade ≤ 2 and the team leadership must be notified.

Subjects with Grade 3 asymptomatic laboratory abnormalities in cholesterol, creatine kinase (CK) or triglycerides may continue study treatment.

For grade 4 events permanently discontinue therapy.

9.2 SERIOUS ADVERSE EVENTS (SAE)

A SAE is defined as any AE that:

- Results in death
- Is life threatening (the subject is at immediate risk of dying from the AE)

[figure not shown]
- Requires subject hospitalization or prolongs existing hospitalization
- Results in persistent or significant disability/incapacity
- Is a congenital anomaly/birth defect

Important medical events that may not result in death, be life-threatening, or require hospitalization may be considered a serious adverse event when, based upon appropriate medical judgment, they may jeopardize the subject and may require medical or surgical intervention to prevent one of the outcomes listed in this definition.

If a pregnancy occurs in a subject or partner of a male subject during a clinical study this must also be reported to CytoDyn. The Investigator should discuss the case with the Medical Monitor. Any pregnant subject must be followed up by the Investigator or designee until the child is born. Any AEs of the subject during pregnancy, that meets serious criteria, must be documented and reported CytoDyn, Inc. Participants who become pregnant will be entered into the Antiretroviral Pregnancy Registry (<http://www.apregistry.com>).

9.3 REPORTING OF SERIOUS ADVERSE EVENTS

The Investigator is required to report all SAEs that occur during the time period specified in [Section 9.1.1](#). Once the Investigator becomes aware of an SAE, he/she must report the SAE to Amarex Safety Department within 24 hours:

The Amarex Medical Monitor may request additional supporting documentation as it becomes available, such as lab reports, ECG reports, discharge summary, hospital notes, etc.

The Investigator is also responsible for reporting all SAEs to the appropriate Institutional Review Board (IRB) in accordance with local laws and regulations. The Investigator is responsible for maintaining documentation in the study file that indicates the IRB has been properly notified. Under 21 CFR 312.32(c), the sponsor is required to notify FDA and all participating investigators in an IND safety report (i.e., 7- or 15-day expedited report) of potentially serious risks from clinical trials or any other source as soon as possible, but no later than 15 calendar days after the sponsor receives

the safety information and determines that the information qualifies for reporting. Participating investigators include all investigators to whom the sponsor is providing drug under any of its INDs or under any investigator's IND (21 CFR 312.32(c)(1)).

9.3.1 SAE Follow-Up

All subjects experiencing an SAE, including the discontinued subjects, must be closely followed until sufficient information is obtained to indicate a return to normal status or until the event stabilizes at a level acceptable to the investigator (i.e., recovery, return to baseline status, no further improvement expected, or death).

For each SAE indicated as an unresolved event on the initial report, regardless of whether the subject completed the study or withdrew, the site should submit a follow-up report with updated information.

10 DIRECT ACCESS TO SOURCE DATA/DOCUMENTATION

Subjects will be identified on eCRFs by a unique subject identification number and on source documents by name and date of birth. No personal identifier will be used in any publication or communication used to support this research study. The subject identification number will be used if it becomes necessary to identify data specific to a single subject.

The monitors, auditors, personnel authorized by the Sponsor, the local IRB, and the FDA are eligible to review medical and research records related to this study as a part of their responsibility to protect human subjects in clinical research and will be given direct access to source data and documentation (e.g., medical charts/records, printouts etc.) for source data verification, provided that subject confidentiality is maintained in accordance with local requirements. Access to electronic medical records may be governed by institution policy and each site will be required to ensure access while remaining compliant with institutional requirements.

11 QUALITY CONTROL AND QUALITY ASSURANCE

11.1 MONITORING REQUIREMENTS

In an effort to fulfill the obligations outlined in 21 Code of Federal Regulations (CFR) Part 312 and ICH guidelines which requires the Sponsor to maintain current personal knowledge of the progress of a study, the Sponsor's designated monitor will visit the center(s) during the study as well as maintain frequent telephone and written communication. The Investigator will permit the Sponsor to monitor the study as frequently as is deemed necessary and provide access to medical records to ensure that data are being recorded adequately, that data are verifiable and that protocol adherence is satisfactory.

The Investigator will permit representatives of the Sponsor and/or designated CRO to inspect all eCRFs and corresponding study subject original medical records (source documents) at regular intervals throughout the study. Subject original medical records and other relevant data must be available to support all data recorded in the eCRF. In addition to the original medical records, these data may include but are not limited to, study, laboratory and diagnostic reports, neurological assessment results, quality of life questionnaire, etc.

Site inspections serve to verify strict adherence to the protocol and the accuracy of the data being entered on the case report forms, in accordance with federal regulations. A Monitoring Log will be maintained at each study site which the monitor will sign, date and state the type of visit.

The Investigator should be aware that the study site and subject records may be inspected by the Sponsor and or representatives of the designated CRO, FDA or other regional regulatory authority.

For the IA, a cut-off date for data collection and monitoring will be determined and sites will be requested to provide current information up to the cut-off date.

11.2 ACCEPTABILITY OF CASE REPORT FORMS (CRFs)

Electronic CRFs must be completed for each subject who has signed an informed consent form. For subjects who are screen failures, this would be limited to the screen failure eCRF page. All source documents and eCRFs will be completed as soon as possible after the subject's visit. Corrections to data on the eCRFs will be documented. The Investigator will review eCRFs to indicate that, to his/her knowledge, they are complete and accurate. Electronic CRFs will be

reviewed by the Sponsor's or designated CRO's monitor, who will make a decision as to their acceptability.

11.3 MODIFICATION OF PROTOCOL

The Investigator will not modify or alter this protocol without first obtaining the concurrence of the Sponsor. Approval by the Investigator's IRB must also be obtained prior to implementation of the change, with two exceptions:

1. When necessary to eliminate apparent immediate hazard to the subject; or
2. When the modification does not involve the subject's participation in the trial.

An amendment may also require modification of the informed consent form. The Investigator will provide an approval letter for the amendment and revised informed consent form, if applicable, to the Sponsor. An amendment must be in writing and it must be dated by both the Sponsor and the Investigator. If necessary, the Sponsor will submit protocol amendments to FDA and other appropriate regulatory authorities and notify other Investigators using this protocol.

